9.2. Definition of Serious Adverse Event

If an event is not an AE per definition above, then it cannot be an SAE even if serious conditions are met (eg, hospitalization for signs/symptoms of the disease under study, death due to progression of disease).

A Serious Adverse Event is defined as any untoward medical occurrence that, at any dose:

a. Results in death

b. Is life-threatening

The term 'life-threatening' in the definition of 'serious' refers to an adverse drug experience that places the participant, in the opinion of the initial reporter, at immediate risk of death from the adverse experience as it occurred. This does not include an adverse drug experience that, had it occurred in a more severe form, might have caused death.

c. Requires inpatient hospitalization or prolongation of existing hospitalization

In general, hospitalization signifies that the participant has been detained (usually involving at least an overnight stay) at the hospital or emergency ward for observation and/or treatment that would not have been appropriate in the physician's office or outpatient setting. Complications that occur during hospitalization are AEs. If a complication prolongs hospitalization or fulfills any other serious criteria, the event is serious. When in doubt as to whether "hospitalization" occurred or was necessary, the AE should be considered serious.

Hospitalization for elective treatment of a pre-existing condition that did not worsen from baseline is not considered an AE.

d. Results in persistent or significant disability/incapacity

- The term disability means a substantial disruption of a person's ability to conduct normal life functions.
- This definition is not intended to include experiences of relatively minor medical significance, such as uncomplicated headache, nausea, vomiting, diarrhea, influenza, and accidental trauma (eg, sprained ankle), that may interfere with or prevent everyday life functions but do not constitute a substantial disruption.

e. Is a congenital anomaly/birth defect

f. Other situations (Important Medical Event)

An event that may not result in death, be immediately life-threatening, or require hospitalization, but may be considered serious when, based on appropriate medical judgment, the event may jeopardize the participant and may require medical or surgical intervention to prevent one of the outcomes listed in the above definition. Examples of such events include invasive or malignant cancers (excluding the disease[s] under study in oncology protocols), intensive treatment in an emergency department or at home for allergic bronchospasm, blood dyscrasias, or convulsions that do not result in hospitalization, or development of drug dependency or drug abuse.

9.3. Recording and Follow-Up of Adverse Events and/or Serious Adverse Events

Adverse Event and Serious Adverse Event Recording

- An AE/SAE that begins or worsens after informed consent is signed should be recorded on the Adverse Event Form in the eCRF. Conditions that were present at the time informed consent was given should be recorded on the Medical History Form in the eCRF.
- When an AE/SAE occurs, it is the responsibility of the investigator to review all documentation (eg, hospital progress notes, laboratory reports, and diagnostics reports) related to the event.
- The investigator (or delegate) will then record all relevant AE/SAE information in the eCRF.
- It is **not** acceptable for the investigator to send photocopies of the participant's medical records in lieu of completing the AE eCRF page.
- There may be instances when copies of medical records for certain cases are requested. In this case, all participant identifiers, with the exception of the participant number, will be redacted on the copies of the medical records before submission.
- The investigator will attempt to establish a diagnosis of the event based on signs, symptoms, and/or other clinical information. Whenever possible, the diagnosis (not the individual signs/symptoms) will be documented as the AE/SAE. When a clear diagnosis cannot be identified, each sign or symptom should be reported as a separate AE/SAE.

To the extent possible, each AE/SAE should be evaluated to determine:

- The severity grade (CTCAE Grade 1 to 5). See below for further instructions on the assessment of intensity.
- Whether there is at least a reasonable possibility that the AE is related to the study drug: suspected (yes) or not suspected (no). See below for further instructions on the assessment of causality.
- The start and end dates, unless unresolved at final follow-up.
- The action taken with regard to study drug as a result of the AE/SAE(s).
- The event outcome (eg, not recovered/not resolved, recovered/resolved, recovering/resolving, recovered/resolved with sequelae, fatal, unknown).
- The seriousness, as per the SAE definition provided in Section 9.2.
- The action taken with regard to the event. Note: If an AE is treated with a concomitant medication or nondrug therapy, this action should be recorded on Adverse Event Form and the treatment should be specified on the appropriate eCRF (eg, Prior/Concomitant Medications, Procedures and Non-Drug Therapy).

Assessment of Intensity

The severity of AEs will be assessed using CTCAE v5.0 Grades 1 through 5. If an event is not classified by CTCAE, the severity of the AE will be graded according to the scale below to estimate the grade of severity:

The investigator will make an assessment of intensity for each AE and SAE reported during the study and assign it to 1 of the following categories:

- **Grade 1:** Mild; asymptomatic or mild symptoms; clinical or diagnostic observations only; treatment not indicated.
- **Grade 2:** Moderate; minimal, local, or noninvasive treatment indicated; limiting age appropriate activities of daily living.

- **Grade 3:** Severe or medically significant but not immediately life-threatening; hospitalization or prolongation of hospitalization indicated; disabling; limiting self-care activities of daily living.
- **Grade 4:** Life-threatening consequences; urgent treatment indicated.
- **Grade 5:** Fatal.

Assessment of Causality

- The investigator is obligated to assess the relationship between study treatment and each occurrence of each AE/SAE. If reference therapy is used in combination with an Incyte study drug or multiple Incyte study drugs are used, the relationship to each study drug must be assessed (ie, for the Incyte product(s) and for the other product(s) that is used in combination with the Incyte product). If appropriate, the relationship to the combination may be assessed as well.
- A "reasonable possibility" of a relationship conveys that there are facts, evidence, and/or arguments to suggest a causal relationship, rather than that a relationship cannot be ruled out.
- The investigator will use clinical judgment to determine the relationship.
- The investigator will also consult the RSI in the IB and/or Product Information, for marketed products, in his/her assessment.
- Alternative causes, such as underlying disease(s), concomitant therapy, and other risk factors, as well as the temporal relationship of the event to study treatment administration, will be considered and investigated.
- For each AE/SAE, the investigator **must** document in the medical notes that he/she has reviewed the AE/SAE and has provided an assessment of causality.
- With regard to assessing causality of SAEs:
 - There may be situations in which an SAE has occurred and the investigator has minimal information to include in the initial report. However, the causality assessment is one of the criteria used when determining regulatory reporting requirements. **Therefore, it is very important that the investigator always make an assessment of causality for every event before the initial transmission of the SAE.**
 - The investigator may change his/her opinion of causality in light of follow-up information and send a follow-up SAE report with the updated causality assessment.

Follow-Up of Adverse Events and Serious Adverse Events

- The investigator is obligated to perform or arrange for the conduct of supplemental measurements and/or evaluations as medically indicated or as requested by the sponsor to elucidate the nature and/or causality of the AE or SAE as fully as possible. This may include additional laboratory tests or investigations, histopathological examinations, or consultation with other health care professionals.
- New or updated information will be recorded in the originally completed eCRF.
- Any updated SAE data will be submitted to the sponsor (or designee) within 24 hours of receipt of the information.
- Once an AE is detected, it should be followed until it has resolved or until it is judged to be permanent; assessment should be made at each visit (or more frequently if necessary) of any changes in severity, the suspected relationship to the study drug, the interventions required to treat the event, and the outcome.
- When the severity of an AE changes over time for a reporting period (eg, between visits), each change in severity will be reported as a separate AE until the event resolves.

9.4. Reporting of Serious Adverse Events

Regardless of suspected causality (eg, relationship to study drug or study procedure[s]), all SAEs occurring after the participant has signed the ICF through 30-35 days after the last dose of study treatment *or* until the participant starts a new anticancer therapy, whichever occurs earlier) must be reported to the sponsor (or designee) within **24 hours** of learning of its occurrence, unless otherwise specified by the Protocol. The investigator will submit any updated SAE data to the sponsor (or designee) within 24 hours of it being available.

Investigators are not obligated to actively seek AE or SAE information after conclusion of the study participation. However, if the investigator learns of any SAE, including a death, at any time after a participant has been discharged from the study, and he/she considers the event to be reasonably related to the study treatment or study participation, the investigator must notify the sponsor (or designee) within 24 hours of becoming aware of the event.

After the initial AE/SAE report, the investigator is required to proactively follow each participant at subsequent visits/contacts. All SAEs will be followed until resolution, stabilization, the event is otherwise explained, or the participant is lost to follow-up (as defined in Section [7.3](#)).

Prompt notification by the investigator to the sponsor of a SAE is essential so that legal obligations and ethical responsibilities towards the safety of participants and the safety of a study treatment under clinical investigation are met.

If the SAE is not documented in the [IB](#) for the study drug (new occurrence) and is thought to be related to the sponsor's study drug, the sponsor or its designee may urgently require further information from the investigator for reporting to health authorities. The sponsor or its designee may need to issue an Investigator Notification to inform all investigators involved in any study with the same drug that this SAE has been reported. Suspected Unexpected Serious Adverse Reactions will be collected and reported to the competent authorities and relevant ethics committees in accordance with Directive 2001/20/EC, or as per national regulatory requirements in participating countries.

The sponsor has a legal responsibility to notify both the local regulatory authority and other regulatory agencies about the safety of a study treatment under clinical investigation. The sponsor will comply with country-specific regulatory requirements relating to safety reporting to the regulatory authority, IRB/IEC, and investigators.

Investigator safety reports must be prepared for suspected unexpected adverse reactions according to local regulatory requirements and sponsor policy and forwarded to investigators as necessary.

An investigator who receives an investigator safety report describing a SAE or other specific safety information (eg, summary or listing of SAEs) from the sponsor will review and then file it along with the Investigator's Brochure and will notify the IRB/IEC, if appropriate according to local requirements.

Serious Adverse Event Reporting

- Information about all SAEs is collected and recorded on the Adverse Event Form in the eCRF.
- The investigator must also complete the Incyte Serious Adverse Event Report Form, in English. Refer to the Incyte Reference Guide for Completing the Serious Adverse Event Report Form.
- Facsimile or email transmission of the Serious Adverse Event Report Form is the preferred method to transmit this information to the PhV/designee (eg, C3i/Telerx). The original copy of the Serious Adverse Event Report Form and the confirmation sheet must be kept at the study site.
- Follow-up information is recorded on an amended or new Serious Adverse Event Report Form, with an indication that it is follow-up to the previously reported SAE and the date of the original report. The follow-up report should include information that was not provided on the previous Serious Adverse Event Report Form, such as the outcome of the event (eg, resolved or ongoing), treatment provided, action taken with study drug because of the SAE (eg, dose reduced, interrupted, or discontinued), or participant disposition (eg, continued or withdrew from study participation). Each recurrence, complication, or progression of the original event should be reported as follow-up to that event, regardless of when it occurs.
- In rare circumstances and in the absence of facsimile or computer equipment, notification by telephone is acceptable with a copy of the Incyte Serious Adverse Event Report Form sent by overnight mail or courier service. Initial notification via telephone does not replace the need for the investigator to complete and sign the Serious Adverse Event Report Form within the designated reporting time frames.

9.5. Emergency Unblinding of Treatment Assignment

Not applicable.

9.6. Pregnancy

Pregnancy, in and of itself, is not regarded as an AE unless there is suspicion that study drug may have interfered with the effectiveness of a contraceptive medication or method. When a pregnancy has been confirmed in a participant during maternal or paternal exposure to study drug, the following procedures should be followed in order to ensure safety:

- The study drug must be interrupted immediately (female participants only; see Section [6.5.1](#) for the maximum permitted duration of study drug interruption).
- If the female participant is no longer pregnant and meets the treatment continuation criteria within 28 days of the scheduled start of a cycle (or your maximum allowable time off study drug), study treatment may be resumed after approval has been received from the sponsor medical monitor.
- The investigator must complete and submit the Incyte Clinical Trial Pregnancy Form to the sponsor or its designee within **24 hours** of learning of the pregnancy.

Data on fetal outcome are collected for regulatory reporting and drug safety evaluation. Follow-up should be conducted for each pregnancy to determine outcome, including spontaneous or voluntary termination, details of the birth, and the presence or absence of any birth defects, congenital abnormalities, or maternal and/or newborn complications, by following until the first well-baby visit. Pregnancy should be recorded on a Clinical Trial Pregnancy Form and reported by the investigator to the sponsor or its designee. Pregnancy follow-up information should be recorded on the same form and should include an assessment of the possible causal relationship

to the sponsor's study drug to any pregnancy outcome, as well as follow-up to the first well-baby visit or the duration specified in local regulations, whichever is later. Refer to the Incyte Reference Guide for Completing the Clinical Trial Pregnancy Form.

Any SAE occurring during pregnancy of a study participant must be recorded on the Serious Adverse Event Report Form and submitted to the sponsor or designee.

Abnormal pregnancy outcomes (eg, spontaneous abortion, fetal death, stillbirth, congenital anomalies, or ectopic pregnancy) are considered SAEs (if occurring in the study participant) and must be reported as described in Section 9.4. If an abnormal pregnancy outcome is reported in a study participant's partner, the event should be reported to the sponsor on the Clinical Trial Pregnancy Form.

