6.5.1. Criteria and Procedures for Dose Interruptions and Adjustments of Study Drug

Safety concerns should be discussed with the sponsor immediately upon occurrence or awareness to determine if the participant should continue or discontinue study treatment.

Treatment with pemigatinib may be delayed up to 2 weeks (14 days) to allow for resolution of toxicity. Participants may resume treatment if no medical condition or other circumstance exists that, in the opinion of the investigator, would make the participant unsuitable for further participation in the study. The treating investigator should contact the sponsor to discuss the case of any participant whose treatment has been delayed for more than 14 days before restarting treatment with pemigatinib. Refer to [Table 10](#) for guidelines.

Table 10: Guidelines for Interruption and Restarting of Study Drug

ADVERSE EVENT	ACTION TAKEN
Chemistry	

 AST and/or ALT is $> 5.0 \times$ ULN. Note: In participants with liver metastasis-related elevations at baseline, contact sponsor to discuss clinical management and possible dose reductions. 	
Step 1: Interrupt pemigatinib up to 2 weeks (14 days) until the toxicity has resolved to \leq Grade 1 except by approval of the medical monitor.
 
Step 2: Restart pemigatinib at same dose. If assessed as related to pemigatinib, restart pemigatinib at next lower dose; monitor as clinically indicated.

Other toxicities	

 Any Grade 1 or Grade 2 toxicity. 	Continue pemigatinib treatment and treat the toxicity; monitor as clinically indicated.

 Any Grade 3 toxicity, if clinically significant and not manageable by supportive care. 	
Step 1: Interrupt pemigatinib up to 2 weeks (14 days), until toxicity resolves to \leq Grade 1.
 
Step 2: Restart pemigatinib at same dose. If assessed as related to pemigatinib, restart pemigatinib at next lower dose; monitor as clinically indicated.

 Any recurrent Grade 3 toxicity after 2 dose reductions. 	Discontinue pemigatinib administration and follow-up per Protocol (exceptions require approval of sponsor).

 Any other Grade 4 toxicity. 	Discontinue pemigatinib administration and follow-up per Protocol.

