6.5.4. Criteria for Permanent Discontinuation of Study Drug

The occurrence of unacceptable toxicity not caused by the underlying disease will require that the study drug be permanently discontinued. Unacceptable toxicity is defined as follows:

- Occurrence of an AE that is related to study drug that, in the judgment of the investigator or the sponsor's medical monitor, compromises the participant's ability to continue study-specific procedures or is considered to not be in the participant's best interest.
- An AE requiring more than 2 dose reductions.
- Persistent AE requiring a delay of therapy for more than 2 weeks (14 days) unless a greater delay has been approved by the sponsor.
- Increase in QT/QTc to > 500 milliseconds or to > 60 milliseconds over baseline. In case of a QTc > 500 milliseconds, the participant must be hospitalized and continuous ECG monitoring must be set up until the measure of the QTc interval decreases below 500 milliseconds and is acceptable in the opinion of the local cardiologist.

See Section [7](#) for discontinuation procedures.

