7. DISCONTINUATION OF STUDY TREATMENT AND PARTICIPANT DISCONTINUATION/WITHDRAWAL

7.1. Discontinuation of Study Treatment

7.1.1. Reasons for Discontinuation

Participants **must** be discontinued from study treatment for the following reasons. Please note that if a participant discontinues study treatment for reasons other than disease progression or withdraw of consent, the participant should be followed until disease progression is documented.

- The participant becomes pregnant.
- Consent is withdrawn.
Note: Consent withdrawn means that the participant has explicitly indicated that they do not want to be followed any longer; in this case no further data, except data in public domain, may be solicited from or collected on the participant. Participants may choose to discontinue study treatment and remain in the study to be followed for progression and survival.
- Further participation would be injurious to the participant's health or well-being, in the investigator's medical judgment.
- Unacceptable toxicity as noted in Section [6.5.4](#).
- The study is terminated by the sponsor.
- The study is terminated by the local health authority, IRB, or IEC.
- Disease progression has been reported by radiology review.
- Other antineoplastic treatment is initiated, not including palliative radiation.

A participant **may** be discontinued from study treatment as follows:

- If, during the course of the study, a participant is found not to have met eligibility criteria, the medical monitor, in collaboration with the investigator, will determine whether the participant should be withdrawn from study treatment.
- If a participant is noncompliant with study procedures or study drug/treatment administration in the investigator's opinion, the sponsor should be consulted for instruction on handling the participant.

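### Section 7.1.1 makes pregnancy a mandatory reason to discontinue study treatment, while Section 9.6 orders interruption and allows a restart, with a time limit that does not match its own cross-reference

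*Protocol*

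**What the plan says.** **Protocol, Section 7.1.1 (Reasons for Discontinuation).** Participants must (the word is in bold) "be discontinued from study treatment for the following reasons". The first entry on that list is "The participant becomes pregnant". It carries no exception and no pointer to Section 9.6. A separate list follows of circumstances in which a participant may be discontinued.

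**Protocol, Section 9.6 (Pregnancy).** For a confirmed pregnancy the first instruction is "The study drug must be interrupted immediately", for female participants only, with a reference to Section 6.5.1 "for the maximum permitted duration of study drug interruption". The next bullet covers a participant who is no longer pregnant and meets the continuation criteria "within 28 days of the scheduled start of a cycle (or your maximum allowable time off study drug" (the closing bracket follows in the text). In that case, "study treatment may be resumed after approval has been received from the sponsor medical monitor".

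**Protocol, Section 6.5.1.** "Treatment with pemigatinib may be delayed up to 2 weeks (14 days) to allow for resolution of toxicity". The investigator is to contact the sponsor before restarting anyone delayed for longer than 14 days. The section does not mention pregnancy.

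**Protocol, Section 8.3.6.1 (Pregnancy Testing).** A positive urine test followed by a negative serum test leaves resumption to the investigator's benefit/risk judgment. For a pregnancy confirmed by serum test, the reader is sent to Section 9.5.

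**The concern.** Two sections prescribe a treatment action for the same event, and the actions differ. Under Section 7.1.1 a confirmed pregnancy ends study treatment. Under Section 9.6 it pauses treatment, and a restart is possible. Two sites could each follow the protocol and act in opposite ways, and either could be cited for a deviation from the other section.

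Two things are at stake. The first is whether a participant who has been pregnant during the study may be given the drug again, which should have one answer. The second is the data record: one site would enter a discontinuation with an end-of-treatment visit, another a dose interruption. Disposition and exposure summaries would then describe the same event in different ways.

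The time limit in Section 9.6 adds a smaller difficulty. It differs from the figure in the section it cites, and it stands beside wording addressed to a protocol author rather than to a site.

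**Working it through.** No sample size, power or error rate enters this point. The check sets the sections side by side.

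**Step 1: the action on a confirmed pregnancy.**

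| | Section 7.1.1 | Section 9.6 |
|---|---|---|
| Action | Discontinue study treatment (mandatory) | Interrupt study drug |
| Restart | None provided for | Permitted if no longer pregnant, continuation criteria met, medical monitor approves |
| Reference to the other section | None | None |

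**Step 2: can the two be read as successive stages?** They cannot.
- Section 7.1.2 attaches an end-of-treatment visit to discontinuation and has its date recorded in the IRT.
- Section 8.7 ties that visit to permanent discontinuation of the drug.
- Section 8.8.2 moves a participant who stops for a reason other than progression into disease follow-up.
- No text returns a discontinued participant to dosing.

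**Step 3: the time limit.**
- Section 6.5.1: 14 days, counted as length of delay, for resolution of toxicity; it can be exceeded after sponsor contact.
- Section 9.6: 28 days, counted from the scheduled start of a cycle.
- Difference in the stated figures: 28 − 14 = 14 days.

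The two clocks start at different points, so the figures are not directly comparable. As an illustration, assume that the drug is withheld from Day 1 of a 21-day cycle, when the urine test falls due. If Section 9.6 counts from that cycle's start, its window allows 28 days off drug. If it counts from the next scheduled start, it allows 21 + 28 = 49 days. Section 9.6 does not say which cycle is meant.

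**Step 4: does another section settle it?** Section 8.3.6.1 permits resumption only where the serum test is negative, that is, where pregnancy was not confirmed. It sends confirmed cases to Section 9.5, which is Emergency Unblinding and is marked not applicable. Pregnancy is Section 9.6.

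**Step 5: effect on the primary endpoint.** Under Section 10.2 the efficacy evaluable population is every enrolled participant with at least one dose, so she stays in the denominator under either rule. With about 50 participants, one case can move the pooled ORR by at most 1/50 = 2 percentage points. It does so only if the choice between stopping and restarting changes whether she is counted as a responder.

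**The case against.** The best defence is that Section 9.6 is the detailed pregnancy procedure and so qualifies the general list in Section 7.1.1. This does not hold. The entry in Section 7.1.1 is itself specific to pregnancy, stands under a mandatory heading, and has no exception, although a discretionary list was available in the same section. Medical monitor approval does not remove the conflict, because the monitor would be approving something Section 7.1.1 rules out.

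Other parts of the defence stand, and they limit the point. A reader might infer any of the following, and the protocol does not support them:

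- **That three rules give three different actions.** Only Sections 7.1.1 and 9.6 prescribe an action on pregnancy. Section 6.5.1 supplies a time limit, and only through the reference in Section 9.6.
- **That 14 and 28 days contradict each other outright.** The 14 days is not a ceiling. Section 6.5.1 contemplates restart after a longer delay once the sponsor has been contacted, and Section 9.6 already requires sponsor approval. A restart between day 14 and day 28 could satisfy both. What remains is a cross-reference that does not match the figure beside it.
- **That Section 6.5.4 is a further conflicting rule.** Its entry is "Persistent AE requiring a delay of therapy for more than 2 weeks (14 days" and concerns adverse events. Section 9.6 says that pregnancy in itself is not one unless interference with contraception is suspected, so in the ordinary case Section 6.5.4 is not triggered.
- **That the conflict permits dosing during pregnancy.** Both rules stop the drug, and no site can restart it alone.

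The event should also be rare: about 50 previously treated participants with advanced tumours, with contraception required and pregnancy tests at screening, every cycle and end of treatment for women of childbearing potential. Finally, that the bracketed phrase is a leftover drafting note is an inference from its use of the second person, though a natural one.

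**Conclusion.** The contradiction between Sections 7.1.1 and 9.6 is plain in the current text, and nothing else in the protocol resolves it. It is an internal contradiction, not a design choice. The mismatch between the 28 days in Section 9.6 and the 14 days in Section 6.5.1 is real but secondary.

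In size, this affects a rare event and has a negligible effect on ORR. It is still worth correcting, because whether a formerly pregnant participant may restart treatment, and whether the event counts as discontinuation or interruption, should not depend on which section a site reads. This conclusion rests on the protocol text alone and takes no view on which rule is right.

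**What to change.** The sponsor's clinical team should:

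1. Reconcile Sections 7.1.1 and 9.6 into one rule, with each section referring to the other.
2. Align any time limit kept in Section 9.6 with its reference to Section 6.5.1, and state the point from which it is counted.
3. Delete the bracketed drafting note in Section 9.6.
4. Correct the reference in Section 8.3.6.1 from Section 9.5 to Section 9.6.

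The choice of rule and of any limit belongs to the clinical team. The cost is wording in a protocol amendment, which needs IRB/IEC approval under Section 11.1 and could be combined with other changes. No statistical analysis changes.
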